8.2.4. Imaging

Imaging provides a non-invasive means of evaluating tissue-specific changes that may not be detectable by assays performed on blood samples. ^{18}F -FDG PET provides a sensitive way to evaluate tissue-specific inflammatory changes. This is achieved through signal enhancement driven by increased blood vessel permeability and presence of hypermetabolic infiltrating immune cells. Pancreatic ^{18}F -FDG PET signal may be susceptible to drastic changes in blood glucose, and could be affected by clearance changes of the tracer induced by therapeutic intervention. While the DW-MRI signal depends on the water diffusion through tissue and is not affected by the metabolic state of the patient, the T2-MRI signal in soft tissue is dependent upon the degree of localized water content. Respiratory motion artifacts and presence of abdominal fat may present challenges for quantitative MRI. Compared to other imaging modalities, there is more cross-sectional published data on the utilization of MRI in acute pancreatic states. However, more examples in the literature exist where ^{18}F -FDG PET was implemented to longitudinally assess pancreatic inflammation. Thus, both imaging modalities appear promising for the detection of pancreatic inflammation or injury. Taken together, these factors point to the advantage an imaging strategy where both modalities are incorporated, as they may each provide complementary information, or only one may be the primary source of pancreatic injury data due to technical/operational challenges that cannot be fully predicted at this time.

[figure not shown]
8.2.4.1. ^{18}F -FDG-PET

^{18}F -FDG-PET will be performed at baseline (placebo run-in period) and following 12 weeks of study treatment (double-blind treatment period) as a method to measure inflammation in the pancreas.

Although ^{18}F -FDG-PET has not been used to detect subclinical pancreatic inflammation in patients with HTG, it has been utilized to assess low-level pancreatic injury in other settings. We plan to assess subclinical pancreatic injury through ^{18}FDG -PET measures (maximal standardized uptake value, SUV_{max} , SUV_{mean} , and incorporation rates, Ki or Kpatlak at baseline and following 12 weeks of treatment). Although ^{18}FDG -PET has not been used in this particular setting, it has been utilized to assess low-level pancreatic injury in other settings. ^{18}F -FDG PET is a molecular imaging modality that has demonstrated high sensitivity in the *in vivo* detection of glycolytic tissues, including tumors and inflammatory foci. ^{18}F -FDG PET has been applied in a clinical setting to the assessment of inflammation for a variety of indications, including AIP, atherosclerosis and infection ([Ozaki 2008](#), [Shreve 1998](#), [Glaudemans 2013](#), [Tahara 2007](#), [Vos 2006](#)). ^{18}F -FDG PET has shown the capability of measuring longitudinal patient inflammatory response in the context of AIP, where patients who present with pancreatitis symptoms and high baseline pancreatic PET signal were treated with corticosteroids. These studies demonstrated the within-patient normalization of PET signal after treatment (see [Figure 2](#)) ([Lee 2009](#)). While normal pancreas has

[figure not shown]
a PET uptake signal with an $SUV_{mean} = 2.0 \pm 0.5$ (mean \pm SD), patients with AIP show enhanced pancreatic PET uptake with an $SUV_{mean} = 4.0 \pm 1.2$, providing a substantial signal window (SUV = a normalized measure of activity concentration in tissue, SUV_{max} is the maximum SUV within a region of interest). Given the test/re-test variability in PET signal (CV = 15%), a mean ~10% change in mean pancreatic SUV signal should be readily detectable in this study. Studies in patients undergoing corticosteroid treatment for AIP experienced consistent reductions of ~40% pancreatic signal and normalization of ^{18}F -FDG pancreatic uptake (Lee 2009, Shigekawa 2010). A 30% reduction in ^{18}F -FDG pancreas uptake should be deemed as clinically significant. In one study (N=12), 50% of patients with pancreatitis and positive ^{18}F -FDG PET scans showed normal amylase and lipase levels (Shreve 1998), suggesting that ^{18}F -FDG PET may have better sensitivity for detection of pancreatic inflammation than traditional markers of pancreatitis.

Figure 2: ^{18}F -FDG PET showing decrease of signal in areas of AIP inflammation (pancreas, salivary glands and retroperitoneum) after up to 2 months of prednisolone treatment (0.5 mg/kg, baseline on the left, post-treatment on the right) (Lee 2009).

^{18}F -FDG PET has been shown to be able detect inflamed/vulnerable atherosclerotic plaque in the carotid of patients (Figure 3) (Tawakol 2006) and to detect ~15% reductions in signal following 12 weeks of treatment with high-dose statin (versus low dose statin) in N=34 patients (Tawakol 2013). Since the acquisitions with ^{18}F -FDG PET in the present study will include the neck and thoracic regions, it will be possible to assess suspect areas of atherosclerotic plaque in the carotid and aorta of patients. Reduction of signal (target to background ratio - TBR) in these areas would indicate a potential beneficial effect of ANGPTL3 inhibition on atherosclerotic lesions. ANGPTL3 inhibition in rodents has led to reductions in atherosclerotic plaque. Since ^{18}F -FDG-PET can detect inflammation in atherosclerotic lesions, we plan to explore imaging of the carotids and aorta before and after treatment, without any further isotope dosing or radiation exposure.

Figure 3: Axial CT and co-registered PET images from 2 patients. Patient A showed low ¹⁸F-FDG uptake in the region of the carotid plaque, while Patient B had high uptake in the region of the carotid plaque. The uptake difference was consistent with high inflammatory infiltration in the atherosclerotic plaque of patient B compared to patient A as determined from excised tissue samples.

¹⁸F-FDG PET scans (including a low-dose CT scan) result in typical effective radiation doses of 7 to 10 mSv per study for an adult (19 microSv/MBq) (ICRP 80). The maximum recommended allowed effective dose for a research patient in a single year is 50 mSv (21CFR361.1). Two ¹⁸F-FDG PET studies would result in an approximate dose of 20 mSv, or 40% of the recommended maximum allowed dose. Risk and management of radiation exposure will be disclosed to patients in the informed consent form. ¹⁸F-FDG PET will be performed at week 2 and at week 16 (12 weeks after initiation of evinacumab treatment).

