10.2. Justification of Sample Size

Percent change in TG is analyzed based on log (post/pre) transformation, allowing for a normal distribution of the data. Standard deviations (SD) of raw percent changes up to 13% are akin to moderate SD on the log scale (30-40%). For the statistical precision calculations, a log-scale SD of 0.5 was used based on available evinacumab phase 1 data, and is assumed to be conservative. With N=10 patients, the 90% confidence interval (CI) for an estimated mean reduction in triglycerides of 40% is approximately 20% to 55%. With N=12, the CI is 22% to 54%. A sample size of 24 is considered adequate to analyze the percent change in TG in the 3 genetic cohorts. Assuming a 20% drop out rate, approximately 30 patients will be needed to assess TG. Additional patients (up to a maximum of approximately 50 patients) will be enrolled with the intent to explore the effect of evinacumab on development of pancreatitis.

For the FDG-PET uptake signal SUV_{max} , prior data on steroid-treated patients yielded a natural log-scale SD of change of 0.66 ([Shigekawa 2010](#)). This yields 80% power to yield a statistically significant (alpha=0.05, 1-sided) change from baseline within the N=16 evinacumab-treated patients if the TRUE underlying geometric mean ratio (post/pre) is 0.65 (back-transformed from the log-scale; ~35% reduction). For comparison to the N=8 placebo-treated patients, assuming log-scale SD=0.15 for placebo based on reproducibility data, and 0.66 for evinacumab, there is 80% power if the TRUE underlying geometric mean ratio (GMR) of GMR's (evinacumab post/pre divided by placebo post/pre) is 0.64 (~36% reduction).

For the key MRI endpoint "mean f", which is the weighting coefficient between contrasting MRI regions ([Klauss 2015](#)) reported summary statistics which yield an SD estimate at most 5.96 for change from baseline. With this assumed SD, the N=24 patients with evinacumab post- and pre-values have 80% power to yield a statistically significant (alpha=0.05, 1-sided) change from baseline if the TRUE underlying mean change is 3.12 (~30% from baseline 10.5, which was observed by Klauss [[Klauss 2015](#)]). For the between-treatment comparison (N=16 evinacumab vs N=8 placebo), there is 80% power if the TRUE difference is 6.62 (~63% of the 10.5 baseline value observed by Klauss [[Klauss 2015](#)]).

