2.2. Sample Size and Power Considerations

Percent change in TG is analyzed based on log (post/pre) transformation, allowing for a normal distribution of the data. Standard deviations (SD) of raw percent changes up to 13% are akin to moderate SD on the log scale (30-40%). For the statistical precision calculations, a log-scale SD of 0.5 was used based on available evinacumab phase 1 data and is assumed to be conservative. With N=10 patients, the 90% confidence interval (CI) for an estimated mean reduction in triglycerides of 40% is approximately 20% to 55%. With N=12, the CI is 22% to 54%. A sample size of 24 is considered adequate to analyze the percent change in TG in the 3 genetic cohorts. Assuming a 20% drop out rate, approximately 30 patients will be needed to assess TG. Additional patients (up to a maximum of approximately 50 patients) will be enrolled with the intent to explore the effect of evinacumab on development of pancreatitis.

For the FDG-PET uptake signal SUVmax, prior data on steroid-treated patients yielded a natural log-scale SD of change of 0.66 ([Shigekawa 2010](#)). This yields 80% power to yield a statistically significant ($\alpha=0.05$, 1-sided) change from baseline within the N=16 evinacumab-treated patients if the TRUE underlying geometric mean ratio (post/pre) is 0.65 (back-transformed from the log-scale; ~35% reduction). For comparison to the N=8 placebo-treated patients, assuming log-scale SD=0.15 for placebo based on reproducibility data, and 0.66 for evinacumab, there is 80% power if the TRUE underlying geometric mean ratio (GMR) of GMR's (evinacumab post/pre divided by placebo post/pre) is 0.64 (~36% reduction).

[figure not shown]
For the key MRI endpoint "mean f", which is the weighting coefficient between contrasting MRI regions (Klauss 2015), reported summary statistics yielded an SD estimate at most 5.96 for change from baseline. With this assumed SD, the N=24 patients with evinacumab post- and pre-values have 80% power to yield a statistically significant (alpha=0.05, 1-sided) change from baseline if the TRUE underlying mean change is 3.12 (~30% from baseline 10.5, which was observed by Klauss [Klauss 2015]). For the between-treatment comparison (N=16 evinacumab vs N=8 placebo), there is 80% power if the TRUE difference is 6.62 (~63% of the 10.5 baseline value observed by Klauss [Klauss 2015]).

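### Protocol 8.2.4.1 calls a 10% mean change in pancreatic SUV readily detectable on the strength of the 15% test/re-test CV alone; the plan's own PET sizing (SUVmax) reaches 80% power only at about a 35% reduction

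*Protocol*

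**What the plan says.** Protocol 8.2.4.1 (18F-FDG-PET) cites a test/re-test CV of 15% and concludes that "a mean ~10% change in mean pancreatic SUV signal should be readily detectable in this study". The same paragraph sets a threshold for relevance: a 30% reduction in "pancreas uptake should be deemed as clinically significant".

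Protocol 10.2 (Justification of Sample Size) sizes the PET endpoint on SUVmax. Its variability input is that "prior data on steroid-treated patients yielded a natural log-scale SD of change of 0.66". The test is for a "statistically significant (alpha=0.05, 1-sided) change from baseline within the N=16 evinacumab-treated patients", and 80% power is reached "if the TRUE underlying geometric mean ratio (post/pre) is 0.65 (back-transformed from the log-scale; ~35% reduction".

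SAP 2.2 repeats these figures. For the comparison with 8 placebo patients, both documents proceed by "assuming log-scale SD=0.15 for placebo based on reproducibility data, and 0.66 for evinacumab" and state 80% power at a ratio of geometric mean ratios of 0.64, about a 36% reduction.

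SUVmax and SUVmean are both secondary endpoints (Protocol 4.2.2; SAP 4.7.4). Neither document gives an SD of change for SUVmean in treated patients.

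**The concern.** The two sections give very different accounts of what PET can show. Section 8.2.4.1 bases its figure on repeatability alone, which amounts to assuming that every treated patient responds by the same proportion. Section 10.2 does not make that assumption: it uses the reproducibility figure for placebo patients and a value more than four times as large (0.66 against 0.15) for treated patients.

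What is at stake is how a PET result is read. Whether imaging biomarkers respond to evinacumab is part of a key secondary aim (Protocol 3.2.1). A reader who relies on 8.2.4.1 would take a result close to no change as informative about effects as small as 10%. The sizing section gives no basis for that.

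**Working it through.** **Inputs.** From Protocol 10.2 and SAP 2.2: log-scale SD of change 0.66 (evinacumab, SUVmax) and 0.15 (placebo); N=16 and N=8; one-sided alpha 0.05. From Protocol 8.2.4.1: effects of 10% (ratio 0.90) and 30% (ratio 0.70), and CV 15%. SAP 5.7.4 names the paired t-test for normally distributed PET endpoints.

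**Formula.** Power of a one-sample t-test on log(post/pre), from the noncentral t distribution with N−1 degrees of freedom and noncentrality |ln(ratio)| / (SD/√N).

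**Reproducing the plan.** Standard error = 0.66/√16 = 0.165. At ratio 0.65, noncentrality = 0.431/0.165 = 2.61 and power = 80.1%, which matches the stated 80%. Between arms, the standard error = √(0.66²/16 + 0.15²/8) = 0.173. At ratio 0.64, noncentrality = 0.446/0.173 = 2.58 and power = 79.7% (Welch), which also matches.

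**Same method, SUVmax SD 0.66, at the two effects in 8.2.4.1.**

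| Comparison | Power at 10% reduction | Power at 30% reduction |
|---|---|---|
| Within arm, N=16 | 15.0% (noncentrality 0.105/0.165 = 0.64) | 66.2% (0.357/0.165 = 2.16) |
| Between arms, 16 vs 8 | 14.5% | 63.1% |
| Within arm, N=26 | 19.7% | 85.0% |
| Within arm, N=33 | 22.7% | 91.8% |

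The last two rows are assumptions. With 50 enrolled at 2:1, about 33 receive evinacumab in the double-blind period (50 × 2/3 = 33.3); after 20% loss about 26 remain (33.3 × 0.8 = 26.7, rounded down). At SD 0.66, 80% power needs about 244 evinacumab patients for a 10% reduction and 23 for a 30% reduction.

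**What SD the 10% sentence needs.** The documents give none for SUVmean in treated patients, so the range at N=16 is:

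- SD of change 0.15 (the CV taken as the whole SD of change): 85% power.
- SD of change about 0.16: 80% power, the upper limit for that level. If 0.15 of this is measurement error, the room left for variation in response is √(0.1617² − 0.15²) = 0.06 on the log scale.
- SD of change 0.21 (15% taken as a per-scan CV, so 0.15 × √2): 60% power.
- SD of change 0.38: 28% power. This value is an assumption built from the SUVmean spreads in 8.2.4.1. The figures 2.0 ± 0.5 (normal) and 4.0 ± 1.2 (autoimmune pancreatitis) give log-scale SDs of about 0.25 and 0.29. With no correlation between them, √(0.25² + 0.29²) = 0.38.

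**What a flat result would exclude.** At SD 0.66 and N=16, an observed ratio of 1.0 has a one-sided 95% lower bound of exp(−1.753 × 0.165) = 0.749 and a two-sided 95% lower bound of exp(−2.131 × 0.165) = 0.703.

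**The case against.** The strongest reply is that the SD of 0.66 belongs to SUVmax in steroid-treated patients, while the 10% sentence concerns mean SUV, which may vary less. This stands. The 15% and 66% are powers for SUVmax and must be labelled so. With the illustrative SUVmean SD of 0.38, power at 30% would be 97% at N=16, so the 66% should not be carried over to SUVmean. The 10% sentence gains little from this, since its power at the same SD is 28%.

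Second, N=16 is the lower end of the range. Enrolment may reach about 50, and with 23 or more evaluable evinacumab patients the 30% threshold has at least 80% power even at SD 0.66. That also stands. It does not help the 10% figure at SD 0.66, which stays under 25%.

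Third, the practical weight is limited. Protocol 10.1 plans no formal hypothesis testing, SAP 5.7.4 treats PET p-values as descriptive, no decision rule uses the 10% sentence, and readily detectable is never defined as a power level. Section 10.2 already prints the 35% and 36% figures. All of this is correct and limits the point to one of wording.

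A reader might also infer that the trial cannot rule out even a 30% reduction. The documents do not support that. Power below 80% is not the same as being unable to exclude an effect: on the plan's own SD and N, an observed ratio of 1.0 would have lower bounds of 0.749 and 0.703, both above 0.70.

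**Conclusion.** The point holds as a mismatch between a stated detectability figure and the plan's own sizing. The 10% claim is not supported: at N=16 it reaches 80% power only if the SD of change is about 0.16 or less, which leaves almost no room for patients to differ in response, and the documents give no SUVmean figure that would justify this. On the SUVmax SD that the plan does use, a true 10% reduction would be missed about 85% of the time at N=16 and about 77–80% of the time at 26 to 33 patients.

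For the 30% threshold the conclusion is milder and depends on N: 66% power for SUVmax at 16 evaluable evinacumab patients, and 85–92% at an assumed 26 to 33. These figures rest on a one-sided 0.05 t-test on the log scale and on the steroid-treated SD carrying over to evinacumab, as the plan itself assumes. They do not show that the trial is unable to exclude a 30% effect, and they say nothing firm about power for SUVmean.

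**What to change.** Change Protocol 8.2.4.1 only:

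- Delete the 10% sentence, or replace it with a cross-reference to the 10.2 result (80% power at about a 35% within-arm reduction, N=16, one-sided 0.05), labelled as SUVmax.
- State the power for SUVmax at the 30% threshold with its N: 66% at 16 evaluable evinacumab patients and, if the sponsor expects more, the figure for that number (85% at 26, 92% at 33).
- Say that the 15% CV describes repeat scans without treatment and does not include variation in response.
- Keep a detectability claim for SUVmean only if an SD of change for SUVmean in treated patients is stated with its source and the power it gives.

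SAP 2.2 needs no change, because it does not contain the 10% sentence and already has the 35% figure. The cost is a few lines of protocol text and a less favourable stated sensitivity. Sample size, endpoints and analysis are unaffected.

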8.2.4.2. Magnetic Resonance Imaging

MRI will be used to assess pancreatic injury/inflammation at baseline and after treatment with evinacumab. With MRI, there is no ionizing radiation dose to the patient that would limit the number of imaging studies that could be performed. Pancreatic MRI is planned for day -28, week -2, week 12 and week 24. Week 12 and 24 scans will allow for short-term and long-term inflammatory response assessments (Klauss 2015). During early stages of pancreatic injury or inflammation, acinar cell injury, activation of pancreatic stellate cells and an invasion by leukocytes, neutrophils and macrophages are all known to exist (Whitcomb 2004). Such intra-and extracellular pathological events modulate microstructural properties of affected pancreatic tissue, and in turn, alter the Brownian motion of water molecules in cellular compartment. In DW-MRI, the random diffusion of water molecules occurring within intracellular, extracellular and intravascular spaces is measured, enabling detection of macroscopic soft tissue pathology such as edema, necrosis and fibrosis. The apparent diffusion coefficient (ADC, units of mm²/sec) is a principal metric quantified in DW-MRI experiments, where ADC values can be mapped across a region of interest at a spatial resolution of ~3 x 3 x 5 mm³. Compared to healthy pancreatic tissue, inflammatory tissue is characterized as having restricted water diffusion (decreased ADCs), while necrotic tissue corresponds to less restricted water diffusion (increased ADCs). Normal pancreas ADCs are (1.77±0.32) X 10³ mm²/sec while acute pancreatitis ADCs are (1.32±0.32) X 10³

mm²/sec showing a significant window for measuring the projected inflammatory changes in the pancreas. Given a test/re-test variability of 18%, a signal change of 20% should be detectable in the present study.

Measurement of ADCs has been used to assess pancreatic health across pancreatic disease states, including acute, chronic and autoimmune pancreatitis as well as pancreatic cancer. Confirming earlier observations, de Freitas Turtulino recently reported a ~20% difference in ADC between healthy (N=15) and mild acute (N=13) pancreas states ([de Freitas Tertulino 2015](#)) ([Figure 4](#)). Lower ADCs were also detected in indications possessing pancreatic inflammation such as in cases of chronic obstruction of the main pancreatic duct known to exist in pancreatic cancer ([Hayano 2016](#)). Here, a ~12% difference in ADCs between large and small main pancreatic duct diameter cohorts was observed (Mann-Whitney U test [P=0.03]). For review of implementation of DW-MRI in pancreatic disease see [Barral 2015](#).

DW-MRI can be combined with T2-weighted and T2 mapping MRI, the latter of which can further inform on the presence, but not clear differentiation of edema, hyperemia or inflammatory cell infiltration within a region of interest ([Figure 5](#)). Moreover, pancreatic lesions can be assessed in combination with whole organ or regional (head, neck, body and tail) pancreatic volume, which can be modulated in a disease state. In the current study, ADCs, T2-weighted intensities and T2 relaxations times will be reported for the whole pancreas in addition for each pancreatic sub-region (head, neck, body and tail). Outside of disease states affecting pancreatic health, a combined diffusion-weighted and T2-MRI approach is commonly utilized for early detection of lesions following stroke, monitoring of hepatic metastases across oncology indications and detection of focal renal lesions known to exist in metabolic diseases such as chronic kidney disease. Thus, the combined DW-MRI and T2-MRI approach is commonly implemented and validated across multiple indications ([Mashhood 2013](#)).

Magnetic resonance imaging is used in the measurement of hepatic fat fraction. A multi-echo gradient-recalled echo sequence acquiring axial images to cover the entire liver is recommended. The echo times shall be such that at successive echo times (TEs), fat and water alternate between out-of-phase and in-phase. To minimize motion artifacts, these should be acquired under breath hold (not to exceed 20 seconds), and 3 separate breath hold acquisitions covering different sections of the liver (superior-middle-inferior) will need to be acquired. The full acquisition should take 3 to 5 minutes.

Figure 4: ADC values as measured by DW-MRI differentiate normal pancreas from acute pancreatic disease states. ~20% difference between normal and mild acute pancreas. Kruskal-Wallis test across cohorts ($P < 0.001$). Sample Size: Normal (N=15), mild acute (N=13) and necrotizing acute (N=8) pancreas (de Freitas Tertulino 2015).

[figure not shown]
[figure not shown]

Figure 5: Axial T2-weighted MRI with fat-suppression demonstrated intrapancreatic threadlike hyperintense structures consistent with interlobular septal inflammation (arrows). Data collected from a 42-year-old male, acute pancreatitis patient (Xiao 2010). Boxplots of the control (N=51) and acute pancreatitis (N=117) groups shows higher T2 values in the patient cohort owing to presence of edematous pancreatic tissue. Calculation of the ROC curve demonstrated good diagnostic value of T2 MRI for diagnosis of acute pancreatitis (Tang 2016).

